## 2. STUDY DESIGN AND STATISTICAL PROCEDURES

We propose to survey HIV negative young adults (age 18-25) waiting to see their providers at Project Stay, a Columbia-affiliated clinic for high-risk youth. After obtaining demographic information, including health insurance status, education level, and sexual health, participants will be asked about their baselines knowledge, attitudes, and willingness to use PrEP. They will then be educated on the recent PrEP results by randomization to either the control group (given a pamphlet on PrEP) or the intervention group (a one-on-one counselor session + the pamphlet on PrEP). Randomization will include stratifying by MSM demographic using a block randomization put together by a third-party. The counselor will be blinded to which arm the participant will be randomized to until the survey has been completed. After their educational intervention, they will see their provider, who will be asked if the participants inquired about PrEP or if the provider brought up the subject him or herself, and if the participant had asked for a prescription. One week following their appointment, they will be e-mailed an electronic survey asking them the same questions on their knowledge, attitudes, and willingness to use PrEP. Finally, we will assess the number of prescriptions for PrEP that were prescribed/filled at 0 months, 6 months, and 1 year. In addition to elucidating baseline willingness to use PrEP and how different modes of education can influence knowledge, interest, and uptake, we also aim to measure the acceptability of other methods of HIV prevention, including alternative ways to administer PrEP, including vaginal and rectal microbicides, IM injection, intermittent oral PrEP use, condoms, circumcision, and vaccines.

The primary research questions are as follows:

Primary Objective #1: To determine if one-on-one counseling on recent PrEP results can increase the proportion of high-risk adolescent and young adults who ask their providers for PrEP

Primary Objective #2: To determine if one-on-one counseling on recent PrEP results can increase the proportion of high-risk adolescent and young adults who are prescribed PrEP and have filled prescriptions at 0, 6, and 12 months.

Secondary Objective #1: To determine current knowledge, attitudes, and willingness to use PrEP for HIV prevention amongst high-risk adolescents and young adults age 18-25 in light of recently announced oral PrEP study results.

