Secondary Objective #2: To determine specific concerns or barriers (e.g., concerns about potential side effects, concerns that I would increase risk taking behavior, don't feel that I am at risk for HIV, don't like taking pills, don't think the pill will protect me from getting HIV infected, concerns that if HIV medications are used now, they won't work in the future if I became HIV+, concerns that others might think I am HIV positive, concerns this would limit the availability of HIV medications for people infected with HIV, already using a strategy for prevention that is effective, concerned it is too expensive) that would prevent high-risk adolescents and young adults to use oral PrEP, and how this may be influenced by different modes of education.

Secondary Objective #3: To assess the acceptability of various methods of HIV prevention, including variations in the timing and way of administering PrEP (i.e. via IM, via microbicides, or intermittent dosing).

Statistical analysis of the questionnaire survey data will be performed using SAS software. Frequencies of responses to survey questions will be described. Chi square and Fisher's exact tests will be computed to compare pamphlet-educated participants' survey responses and PrEP prescriptions to the responses and prescriptions of participants educated by one-on-one counseling. Variables with p-value < 0.05 will be considered significant and will be included in multivariate logistic regression model. Forward selection will be used in the logistic regression model to evaluate variables independently associated with willingness to use PrEP. The outcome variables, whether or not they would use PrEP and bring the issue up with their provider, will be evaluated using a proportion and compared between groups; PrEP prescriptions written and filled at 0, 6, and 12 months will also be evaluated, proportion will be computed and then compared between groups.

The primary endpoint is the difference between the proportion of participants who asked their providers about PrEP in the intervention group versus control group. Because of the limited ability to survey 100 participants (50 in each group), we will use this fixed number of subjects in our power analysis to determine the smallest difference for which the available number of subjects will lead to statistical significance.

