### 3. STUDY PROCEDURES

After screening for HIV-negative patients ages 18-25 waiting to be seen by providers at Project Stay, informed consent will be given about the study. If the patient decides to participate in the study and agrees to the informed consent, the initial survey will be distributed either in hard-copy form or on an iPad (using a computer-assisted self-interview assessment) to obtain the data. Following the survey, the counselor will see whether or the patient is MSM, and perform stratified randomization based off this demographic. A third-party statistician will provide assignments in premade envelopes assigning participants based off blocked and stratified randomization to each arm of the study, which will not be opened until the participants has completed the survey. If the participant is assigned the control arm,

s/he will receive a pamphlet on the recent PrEP studies and asked to read over the information prior to seeing their provider. If the participant is assigned the interventional arm, the counselor will provide a one-on-one session on the recent PrEP results and answer any questions they might have, in addition to receiving the aforementioned pamphlet. All participants will then be asked to bring a sealed envelope to the provider, which will have three questions that the provider will fill out after their encounter with the patient:

1. Did the patient ask you about PrEP?
2. Did you bring up the subject of PrEP with the patient?
3. If yes to either, approximately how much time did you spend talking to the patient about PrEP?
4. Did the patient ask for a prescription for PrEP?

One week following the initial survey, participants will be contacted via e-mail about completing the final part of the study, which will include some of the same questions regarding knowledge, attitudes, and willing to use PrEP, as well as acceptability of other HIV prevention methods. This survey will be given using Survey Gizmo, a secure online survey provider service. Reminder e-mails will be sent up to 3 times, with a phone call follow up if the survey has not yet been completed. Participants will received a \$5 gift certificate to either Starbucks or McDonalds for completing the first portion of the study, and another \$5 gift certificate for completing the second/final part of the study.

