#### 5. STUDY INSTRUMENTS

We will be distributing an initial questionnaire (either in electronic or hard-copy format) to collect data on:

1. Patients' demographic information, sexual behavior and health, and drug use
2. Patients' baseline knowledge, attitudes, and willingness to use oral PrEP
3. Patient's acceptance of other methods of prevention HIV methods

The second questionnaire (e-mailed to the patients using SurveyGizmo) will ask the same questions in 2 and 3 as above.

Questionnaires attached:

1. Initial Survey to Assess Knowledge, Attitudes, and Willingness to Use PrEP Among High-Risk Adolescents and Young Adults.doc
2. Follow-up Survey to Assess Knowledge, Attitudes, and Willingness to Use PrEP Among High-Risk Adolescents and Young Adults.doc

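### The between-arm test of the one-week survey answers makes no use of the pre-randomisation answers or the MSM stratum: a cheap gain in precision, mainly for secondary outcomes

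*Protocol*

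**What the plan says.** All references are to the protocol.

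- **Before randomisation.** Section 2: "participants will be asked about their baselines knowledge, attitudes, and willingness to use PrEP". Section 3 keeps the assignment envelope closed, "which will not be opened until the participants has completed the survey". The first answers are therefore true baseline values.
- **At one week.** Section 2: "they will be e-mailed an electronic survey asking them the same questions on their knowledge, attitudes, and willingness to use PrEP". Section 5 agrees: "The second questionnaire (e-mailed to the patients using SurveyGizmo) will ask the same questions in 2 and 3 as above". Section 3 is narrower and describes a survey "which will include some of the same questions regarding knowledge, attitudes, and willing to use PrEP".
- **Comparison of arms.** Section 2: "Chi square and Fisher's exact tests will be computed to compare pamphlet-educated participants' survey responses and PrEP prescriptions" with those of the counselled arm. On the outcomes it adds: "The outcome variables, whether or not they would use PrEP and bring the issue up with their provider, will be evaluated using a proportion", followed by a comparison between groups.
- **The only multivariable model.** Section 2 plans a logistic regression for correlates of willingness. Variables enter after a p < 0.05 screen and by forward selection. Neither arm, the baseline answer nor the MSM stratum is named as a term that must be in it.
- **Design.** Randomisation is blocked and stratified by MSM status only. The sample is fixed at 100, 50 per arm, for reasons of feasibility.

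**The concern.** Each participant answers the repeated items twice, once before and once after the education. The stated test of the arms uses only the second answer. Where the two answers are correlated, part of the one-week variation is already explained by what the person said at the start, and an unadjusted test counts that part as noise.

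Two features of this trial make that worth changing. The sample cannot grow, so precision left in the baseline data cannot be recovered by recruiting more people. Baseline willingness is also not a stratification factor, so nothing in the design balances it. At stake is how sharply the trial can answer its question on whether the mode of education shifts knowledge, interest and perceived barriers (Section 2, including Secondary Objective #2).

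**Working it through.** **Inputs from the protocol (Section 2).** 50 per arm; alpha 0.05 (taken as two-sided, since limits are given in both directions); power 0.80; intervention proportion 0.74; control limit 0.46; detectable difference 0.28. The protocol derives these for asking the provider, starting from a 74% willingness figure. They are used here as an illustration for one-week willingness, because no survey item has its own power statement.

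**Assumed.** The correlation rho between baseline and one-week answers, over 0 to 0.7, and baseline prevalences of 0.3 to 0.7. The protocol gives neither.

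**Step 1: the protocol's own figure.** With the conservative variance 0.25 per observation, the detectable difference is (1.96 + 0.84) × 0.5 × √(2/50) = 0.280, which matches 0.28. With the usual pooled-variance formula it is 0.271, and with a continuity correction 0.291. The stated figure is sound.

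**Step 2: unadjusted power at 0.74 v 0.46.** Mean proportion 0.60. z = [0.28 × √50 − 1.96 × √(2 × 0.60 × 0.40)] / √(0.74 × 0.26 + 0.46 × 0.54) = (1.980 − 1.358) / 0.664 = 0.937, so power is 0.826. The standard error of the difference is √(0.1924/50 + 0.2484/50) = 0.094.

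**Step 3: adjustment for the baseline answer.** Linear adjustment multiplies the variance by 1 − rho², which is equivalent to 50/(1 − rho²) per arm.

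| rho | 1 − rho² | SE | Equivalent n per arm | Power, 0.74 v 0.46 | Power, 0.74 v 0.54 | Detectable difference |
|---|---|---|---|---|---|---|
| 0 | 1.00 | 0.094 | 50 | 0.83 | 0.55 | 0.271 |
| 0.1 | 0.99 | 0.093 | 51 | 0.83 | 0.55 | 0.269 |
| 0.3 | 0.91 | 0.090 | 55 | 0.86 | 0.59 | 0.258 |
| 0.5 | 0.75 | 0.081 | 67 | 0.92 | 0.68 | 0.233 |
| 0.7 | 0.51 | 0.067 | 98 | 0.98 | 0.84 | 0.190 |

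The last row is near the ceiling for yes/no answers. Two such answers with proportions p < q can correlate at most √[p(1 − q) / (q(1 − p))]. Against 74% at follow-up, a 50% baseline allows at most √(0.5 × 0.26 / (0.74 × 0.5)) = 0.59. A 60% baseline allows √(0.6 × 0.26 / (0.74 × 0.4)) = 0.73.

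**Step 4: simulation.** 8,000 trials per setting, 50 per arm, baseline prevalence 0.5, linear model with robust standard errors. At rho = 0.5 the empirical SE was 0.094 unadjusted and 0.082 adjusted, and power was 0.83 and 0.92. With no true effect, the rejection rate was 0.055 and 0.052. Both estimates centred on the true difference. At rho = 0.3 adjusted power was 0.86, and at rho = 0 nothing was gained (0.83 in both analyses). rho = 0.7 was not simulated.

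**Step 5: chance imbalance.** By the exact binomial with 50 per arm, the two arms differ by 10 points or more on a yes/no baseline item with probability 0.33 at prevalence 0.3 or 0.7, and 0.37 at 0.5. At rho = 0.5 and baseline prevalence 0.5, a 10-point gap moves the unadjusted one-week difference by 0.10 × 0.5 × √(0.46 × 0.54)/0.5 = 0.050 on the control-arm variance, or 0.10 × 0.5 × √(0.74 × 0.26)/0.5 = 0.044 on the intervention-arm variance. That is 4 to 5 points.

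**The case against.** The strongest reply is that this is a preference for efficiency and not an error. The baseline answers precede allocation, so the unadjusted comparison of randomised arms is valid, and the nominal error rate already allows for chance imbalance. That stands. A reader might infer that the plan mistakes baseline differences for an effect of counselling. Randomisation rules that out on average, and the simulated error rates show no inflation of consequence.

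A reader might also infer a bias from non-response to the e-mailed survey. The protocol gives no response rate and provides up to three reminders, a telephone call and a second gift certificate. Adjustment would in any case help only to the extent that baseline answers explain who responds. Nothing here supports a claim of bias.

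The scope is limited too. The primary endpoint, asking the provider about PrEP, is recorded after the visit and has no baseline value, nor do prescriptions. The outcome sentence quoted from Section 2 covers both willingness and raising the subject with the provider, so only its first half has a baseline counterpart. It would also be too strong to say that baseline answers are shut out altogether. The logistic model could select one, but only by a significance rule, which is not a pre-specified adjusted arm effect. A fuller covariate list could sit in an SAP that is not shown, but the protocol itself names the unadjusted tests, so the point is about a stated method.

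Finally, the correlation may be low. Section 1 reports limited prior knowledge of PrEP, and the education is meant to change the answers.

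**Conclusion.** The point holds as a low-cost improvement, mainly to the secondary survey outcomes. The stated analysis is valid but less precise than the collected data allow. At 74% v 46% with 50 per arm, power goes from about 0.83 to 0.86 at an assumed correlation of 0.3 and to 0.92 at 0.5. The 0.98 at 0.7 is an upper-end figure, and at 0.1 or below there is almost no gain. Protection against a chance baseline gap of 10 points or more, which arises in about a third of trials for a given yes/no item, is the other benefit.

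These sizes rest on the assumed correlations, on complete follow-up of 50 per arm and on borrowing the protocol's primary-endpoint proportions. They apply only to items asked at both times. Sections 2 and 5 imply full repetition and Section 3 only partial repetition, so the list of repeated items needs settling.

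**What to change.** In Section 2, replace the unadjusted test of repeated survey items with a pre-specified model:

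- For each item asked at both times, fit one-week answer on arm, the same item's baseline answer and MSM stratum, with all three forced in.
- Report the adjusted difference in proportions with its 95% confidence interval, either by standardisation from a logistic model or from a linear model with robust standard errors. This keeps the scale that Section 2 already uses, which a conditional odds ratio would not.
- Keep Fisher's exact test for sparse items, such as rarely endorsed barriers, where a model may be unstable or fail to converge.
- Keep the forward-selected model, if wanted, as a separate exploratory look at correlates of willingness.
- Optionally, add baseline willingness as a covariate in a supportive analysis of asking the provider.
- State which items are repeated, so that Sections 2, 3 and 5 agree.

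The cost is a change of wording and slightly more analysis work. No new data, visits or participants are needed. The drawback is model instability for rare items, which the retained exact test covers.

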A study in Boston found that 74% of MSM were interested in using PrEP after being educated in-person about its potential (12). Based off this information, one can assume that the proportion of those willing to use PrEP will be approximately 74% for the group with one-on-one counseling (+ pamphlet) on the recent PrEP results, and could lead to a corresponding 74% who will ask their providers about it. Using backward power calculation using our predetermined sample size of 50 in each group, with  $\alpha = .05$  and power = .80, we would find a difference between the two groups if the proportion of those who ask their provider about PrEP in the control group is < .46 (or > .96). Thus, the smallest difference for which our study will find a statistical difference between each group is .28.

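### Randomisation is stratified by MSM status but the stated between-arm comparisons ignore the stratum, which can cost precision if MSM status is prognostic

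*Protocol*

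**What the plan says.** On allocation, Protocol section 2 states: "Randomization will include stratifying by MSM demographic using a block randomization put together by a third-party". Section 3 repeats it: once the baseline survey is done, the counselor establishes whether the patient is MSM in order to "perform stratified randomization based off this demographic", using envelopes prepared by a third-party statistician.

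On analysis, section 2 states: "Chi square and Fisher's exact tests will be computed to compare pamphlet-educated participants' survey responses and PrEP prescriptions" between the two education arms. It defines the primary endpoint separately: "The primary endpoint is the difference between the proportion of participants who asked their providers about PrEP in the intervention group versus control group". For that outcome it says only that it "will be evaluated using a proportion and compared between groups", without naming a test.

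The one multivariable model is exploratory: "Forward selection will be used in the logistic regression model to evaluate variables independently associated with willingness to use PrEP". It concerns willingness rather than the primary endpoint, and it does not force MSM status in.

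The power statement uses a "predetermined sample size of 50 in each group", alpha .05, power .80 and an intervention rate of 74%. It gives a smallest detectable difference of .28 (control below .46). No comparison in the document mentions the randomisation stratum.

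**The concern.** Blocking within MSM strata makes the arms nearly equal in their MSM mix, so differences between strata drop out of the comparison of arms. A simple two-by-two test does not use this. Its standard error is built from the overall proportions and still contains the between-stratum part. If MSM and non-MSM participants differ in how often they ask about PrEP, the standard error is too large, the interval too wide, and the test can reject less often than its nominal level.

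Section 2 fixes the sample at 100 because that is all the study can survey. Lost precision therefore cannot be bought back with more participants.

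**Working it through.** **1. Inputs from the protocol.** 50 per arm; alpha .05, taken as two-sided because the power statement gives limits on both sides of 74%; power .80; rates .74 and .46.

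**2. The protocol's own figure.** Use the two-proportion formula with the pooled variance throughout, n = 2p̄q̄(1.960 + 0.842)²/d², where p̄ = (.74 + .46)/2 = .60 and d = .28. Then n = 2 × .60 × .40 × 7.849/.0784 = 48.05, so 49 per arm. At 50 per arm, √(2 × .60 × .40/50) = .098 and power is Φ(.28/.098 − 1.960) = .815. The stated .28 is reproduced, and it is an unstratified calculation. Exact power at 50 per arm is .832 for chi-square and .775 for Fisher.

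**3. Assumptions, not in the protocol.** The share of MSM is taken as 50% (25 MSM and 25 non-MSM per arm), with a range of 30% to 70% checked. The odds ratio linking MSM status to asking is varied from 1 to about 17 and is the same in both arms. The overall rates stay at .46 and .74.

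**4. Where the excess standard error comes from.** Take control rates of .66 and .26 in the two strata, a gap of .4. The odds ratio is (.66/.34)/(.26/.74) = 5.5. The same odds ratio with an overall rate of .74 gives .889 and .591 in the counseling arm.
- Within-stratum variance, control: (.66 × .34 + .26 × .74)/2 = .2084.
- Within-stratum variance, counseling: (.889 × .111 + .591 × .409)/2 = .170.
- True SE of the difference: √((.2084 + .170)/50) = .087.
- Unstratified SE from the overall rates: √((.46 × .54 + .74 × .26)/50) = √(.4408/50) = .094. Its average over simulated trials is .093.

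The 95% half-width is thus about 1.96 × .094 = .184 where 1.96 × .087 = .171 would do.

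**5. Power and type I error by simulation.** 400,000 trials per setting, 50% MSM, CMH without continuity correction. Type I error is that of the unstratified chi-square with both arms at an overall rate of .46.

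| MSM odds ratio | Power, chi-square | Power, CMH | Gain (points) | Type I error, chi-square |
|---|---|---|---|---|
| 1 | .832 | .832 | 0 | .056 |
| 2 | .835 | .837 | 0.2 | .053 |
| 3 | .840 | .849 | 0.9 | .048 |
| 5 | .848 | .874 | 2.6 | .039 |
| 5.5 (gap .4) | .850 | .880 | 3.0 | .037 |
| 10 | .863 | .913 | 5.0 | .026 |
| 16.6 (gap .6) | .874 | .938 | 6.4 | .017 |

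The type I error of CMH is .050 to .056 throughout. Across MSM shares of 30% to 70% the gain is 0.1 to 0.2 points at an odds ratio of 2, 0.3 to 0.9 at 3, 1.3 to 2.6 at 5, and 3 to 5 at 10.

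**The case against.** The strongest reply is that no loss has been shown for this trial. The protocol does not say how many participants are MSM or whether they ask about PrEP more often, and it describes the whole clinic population as high-risk. For an odds ratio of 3 or less the gain is under one point, and the chi-square test is then close to its nominal level. That stands, and it keeps the point minor.

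It also stands that no test is named outright for the primary endpoint. Chi-square or Fisher is the most natural reading, since these are the only between-arm tests the section names. A statistical analysis plan that is not shown could specify a stratified analysis. But the protocol does describe its comparisons, and nothing in them refers to the stratum.

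Four stronger readings are tempting and are not supported:
- **The test is conservative and power is certainly lost.** This holds only if MSM status is prognostic, and it is visible only when the association is fairly strong.
- **The trial stratified because it expected MSM status to predict asking.** No reason for stratifying is given.
- **The analysis is invalid or the power claim is wrong.** Ignoring the stratum does not inflate type I error. The .056 at an odds ratio of 1 is small-sample discreteness and is the same for CMH. The stated .28 is consistent with an unstratified test.
- **Fisher's low power is further evidence.** Its type I error of .032 to .035 and power of about .775 arise with no MSM effect at all, so they come from discreteness.

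The figures concern the primary endpoint only. None was computed for prescriptions or survey items, where the same reasoning applies but the size is unknown.

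**Conclusion.** The mismatch is real: allocation is stratified by MSM status and the stated comparisons are not. The consequence is a possible loss of precision and a wider interval, conditional on MSM status being prognostic. With 50% MSM and rates of .46 and .74, stratifying gains about 0 to 1 point of power for an odds ratio up to 3, about 3 points near 5, and about 5 to 6 points at 10 to 17. It costs nothing when there is no association. Severity is minor. It is worth acting on because the sample size is fixed and the change does no harm in any setting examined.

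**What to change.** State in Protocol section 2 that the primary comparison, asking the provider about PrEP, is a Cochran-Mantel-Haenszel test stratified by MSM status as used at randomisation, in its exact version if cells are sparse. Report it with a stratified risk difference and 95% CI. Use the same approach for prescriptions written and filled and for the between-arm survey comparisons. Keep the unstratified chi-square and Fisher's exact tests as sensitivity analyses.

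This also names a test for the primary endpoint. The cost is a sentence or two of text and an option in the analysis software. No new data are needed, because MSM status is established for each participant before allocation. The sample size and the stated .28 can stay as they are.
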